1.0 Research Design

1.1 Purpose/Specific Aims

The purpose of this study is to evaluate the efficacy of Nitazoxanide (NTZ), Ribavirin (RBV) and Hydroxychloroquine (HCQ) versus placebo in participants with proven SARS-CoV-2 infection who are asymptomatic or mildly symptomatic with COVID-19. Those with illness requiring hospitalization, or who present with hypoxia (PO2<92%) or shortness of breath at time of enrollment are excluded.

A. Objectives

In participants with proven SARS-CoV-2 infection who are asymptomatic or mildly symptomatic with COVID-19 randomly allocated to nitazoxanide, ribavirin plus hydroxychloroquine (NTZ, RBV + HCQ) or placebo.

Primary Objective:

To assess the rate of decline in viral load over the 10 days after randomization between participants treated with NTZ, RBV + HCQ for COVID-19 and placebo.

Secondary Objective:

- 1. To compare the proportion of participants with virus below LLOQ at day 10
- 2. To compare the proportion of participants who are asymptomatic and symptomatic at day 10
- 3. To compare the time of onset and frequency of the development of fever and other symptoms of COVID-19 in those who were asymptomatic at enrollment
- 4. To compare the progression in severity of COVID-19 symptoms (hospitalization and length of stay; admission to intensive care unit and number of days in unit; intubation, Death (any cause))
- 5. To compare the severity of disease in participants who develop symptoms of COVID-19
- 6. To compare the side effects of NTZ, RBV + HCQ compared to placebo
- 7. To determine whether baseline viral load predicts response to therapy
- 8. To assess the rate of decline in viral load over days 3 and 6 after randomization
- 9. To assess new, self-reported COVID-19 infection in household members

B. Hypotheses / Research Question(s)

We hypothesize that treatment with NTZ, RBV + HCQ decreases viral load and the progression of symptoms, or emergence of symptoms in those who are asymptomatic at baseline, in SARS-CoV-2-positive adults compared to placebo.

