1.3 Research Design and Methods

We will conduct a randomized clinical trial enrolling eligible participants who are determined to be SARS-CoV-2-positive (e.g., via Rutgers Corona Cohort [RCC] study, hospital or other screening programs) who volunteer for the study. Specifically, we will enroll 70 participants whose test has been performed within the past 7 days who are either asymptomatic or mildly symptomatic at baseline. Mild COVID-19 symptoms include new cough, sore throat, fever, myalgias, new vomiting or diarrheaor change in smell or taste. Illness requiring hospitalization, or those who present with hypoxia (PO2<92%) or shortness of breath at time of enrollment will be classified as significantly symptomatic and excluded from study participation. People who are allergic or intolerant to NTZ, RBV or HCQ will be excluded. We will randomly allocate participants stratified by presence of mild symptoms to 1) NTZ, RBV and HCQ or 2) placebo. Treatment with the investigational agents or placebo will continue for 5 days. Viral load will be assessed at baseline (day 0) as well as at days 3, 6, and 10 to monitor response to antiviral treatment. Immune status will be determined by antibody testing of blood collected at baseline and day 28.

Prior to initiating enrollment, we will prepare two randomization tables for treatment assignment using permuted blocks of six which will be provided to the research pharmacist. One table will be used for participants without symptoms and the other will be used for those with mild symptoms. The pharmacist will prepare kits containing the 5-day supply of study medications (investigational drugs/placebo) which will be sequentially numbered in accordance with the randomization tables. The contents of each kit (investigation drugs/placebo) will be indistinguishable. Study staff will establish symptom status at the baseline visit, and per pharmacy order, provide the participant the next numbered medication kit in the participant's stratum (no symptoms/mild symptoms). The study investigators, staff interacting with the participants are all masked to treatment assignment

A. Research Procedures

- 1. Study Procedures:
 - Day 0/1 Screening/Baseline Visit (in person)
 - Pre-screen via online screening form to confirm eligibility
 - Obtain informed consent for trial enrollment
 - Medical history
 - Medication history
 - Document symptoms (if any)

- o Take temperature, PO2, Pulse
- Q-T interval assessment

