- 4. Proportion of participants with progression of severity of COVID-19 symptoms (hospitalization and length of stay; admission to intensive care unit and number of days in unit; Intubation; Death (any cause))
- 5. Comparison of severity of disease in participants who develop symptoms of COVID-19 at all timepoints
- 6. Assessment of medication toxicity as measured by standard metrics
- 7. Q-T interval from baseline of > 60msec or QT > 500 msec)
- 8. Number of participants with undetectable viral load and absence of symptoms
- 9. Rate of decline in viral load at study days 3 and 6
- 10. New, self-reported COVID infection in household members

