6.0 Data Management Plan

6.1 Data Analysis

We will follow intention-to-treat principles and analyze the groups as randomized. A summary table of baseline variables will be created with means and standard deviations for continuous variables or percentages for categorical variables, all stratified by treatment group.

Primary outcome. We will have repeated measures of log10 VL for each participant. These measurements will occur on day 0 (baseline) and at about days 3, 6 and 10. We will fit a linear mixed effects model, where log10 VL is the outcome, indicators for treatment group (SoC reference), time, and treatment by time interactions are the predictors. The model will include a random slope and intercept, to account for within participant correlation. The robust sandwich variance will be used to estimate standard errors. Because we are estimating within participant changes over time from randomization, we can estimate a treatment effect at any particular day. Our primary hypotheses involve the change over time, which we will assess with the treatment by time interaction terms. If participants drop out from the study

before the day 10 visit, we will use all of their preceding data. Linear mixed effects models rely on the assumption that missing data are missing at random.

Secondary outcomes. For binary outcomes, such as progression to having symptoms, intubation, death, hospitalization, and admission to intensive care unit, we will fit logistic regression models. The covariates will include the treatment group indicators. We will report odds ratios and 95% confidence intervals. For change variables, such as change in viral shedding or change in Q-T interval, we will fit linear mixed effects models (similar to primary outcome).

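### Secondary endpoint 5 compares severity only among participants who develop symptoms, a post-randomization group that treatment is hypothesized to change, so the contrast can mislead in either direction

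*Combined protocol and SAP*

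**What the plan says.** Secondary objective 5 (section 1.1 A) is "To compare the severity of disease in participants who develop symptoms of COVID-19". Secondary endpoint 5 (section 1.3 F) is "Comparison of severity of disease in participants who develop symptoms of COVID-19 at all timepoints". Both restrict the comparison to people who develop symptoms.

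The hypothesis in section 1.1 B is that treatment decreases, among other things, "emergence of symptoms in those who are asymptomatic at baseline". Endpoint 3 compares that outcome directly.

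On allocation, section 1.3 states: "We will randomly allocate participants stratified by presence of mild symptoms". Nothing says whether participants with mild symptoms at baseline count as developing symptoms for endpoint 5.

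On analysis, section 6.1 states: "We will follow intention-to-treat principles and analyze the groups as randomized". For secondary outcomes it continues: "For binary outcomes, such as progression to having symptoms, intubation, death, hospitalization, and admission to intensive care unit, we will fit logistic regression models". On those models it adds: "The covariates will include the treatment group indicators". Change variables get linear mixed models. No severity scale, main assessment time or method is named for endpoint 5.

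**The concern.** Randomization makes the arms comparable at entry. It does not make those who later fall ill comparable if treatment affects who falls ill. If the regimen prevents mainly mild cases, the treated participants who still become symptomatic are on average the sicker ones, and the drug can look harmful. If it reduces mild and moderate illness in proportion, the mix among the symptomatic does not change and a real benefit disappears from view.

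Endpoint 5 is also the only endpoint that could grade illness between any symptom and admission to hospital. Endpoints 2, 3 and 8 use symptoms as present or absent, and endpoint 4 is built on hospitalization, intensive care, intubation and death. New shortness of breath or low oxygen saturation without admission falls in the gap. The protocol itself treats that as a clinical boundary at entry: "hypoxia (PO2<92%) or shortness of breath at time of enrollment will be classified as significantly symptomatic".

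**Working it through.** There is no figure in the plan to reproduce: the documents give no symptom rate, effect size or power for endpoint 5. All rates below are assumptions, chosen to show how the contrast behaves.

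**Setup (assumed).** Worst level reached, in the baseline-asymptomatic stratum. Placebo: 35% mild, 15% moderate, 50% none.

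**Moderate share among the symptomatic = moderate / (mild + moderate).**

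| Effect of treatment | Mild | Moderate | Share among symptomatic | Moderate in whole stratum |
|---|---|---|---|---|
| None (placebo) | 35% | 15% | 15/50 = 30% | 15% |
| Mild halved | 17.5% | 15% | 15/32.5 = 46% | 15% |
| Both halved | 17.5% | 7.5% | 7.5/25 = 30% | 7.5% |
| Half of each level moves down one level | 25% | 7.5% | 7.5/32.5 = 23% | 7.5% |

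Row 2 looks like harm when no one is worse. Row 3 looks like no effect when moderate illness has halved. Row 4 points the right way.

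**If participants symptomatic at baseline are counted.** Let f be the fraction of the trial asymptomatic at baseline. Assume 30% of those symptomatic at baseline reach moderate in either arm.

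- Placebo: [0.30(1−f) + 0.15f] / [(1−f) + 0.50f] = 30% for every f.
- Mild halved: [0.30(1−f) + 0.15f] / [(1−f) + 0.325f] = 46% at f = 1, 38% at 0.75, 34% at 0.5 and 32% at 0.25.
- Both halved: [0.30(1−f) + 0.075f] / [(1−f) + 0.25f] = 30% for every f.

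**How often the contrast points against the active arm.** Simulation of 400,000 trials with an assumed 17 per arm in the baseline-asymptomatic stratum (about half of the 35 per arm in section 1.5):

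| Scenario | Symptomatic only | Everyone in stratum, ranked | Any symptom (endpoint 3) |
|---|---|---|---|
| Mild halved | 70% | 19% | 11% |
| Both halved | 45% | 6% | 4% |

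With no treatment effect the symptomatic-only figure is about 48%, the rest being ties or in favour, so 45% means lost information rather than apparent harm. Under the one-level shift the symptomatic-only contrast is against the active arm in 35% of trials and in favour in 59%. If 18 baseline-symptomatic participants per arm are counted as well, the mild-halved figure falls from 70% to about 60%, and the both-halved figure becomes 49%.

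The expected numbers compared are small: 17 × 0.50 = 8.5 on placebo, against 17 × 0.325 = 5.5 (mild halved) or 17 × 0.25 = 4.3 (both halved).

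**Power of a rank test on everyone in the stratum** (two-sided 5%, 40,000 trials): 14% (mild halved) and 31% (both halved) with 17 per arm; 23% and 57% if all 35 per arm were in that stratum.

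**Proportional odds.** With mild halved, the odds ratio for any symptom is (0.325/0.675)/(0.50/0.50) = 0.48, and for moderate it is 1.0. A single common odds ratio would misdescribe this pattern.

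These runs use the worst level reached. A comparison of the level at day 10 was not simulated.

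**The case against.** The strongest reply is that other endpoints already answer the question without conditioning. Under the same assumptions endpoint 3 points the wrong way in only 11% and 4% of trials, slightly less often than the ranked scale. The gain from 70% to 19% comes largely from crediting prevention of symptoms, which endpoint 3 already measures. With mild halved there is no effect on moderate illness to recover: compared in everyone, it is against the active arm in 40% of trials, tied in 19% and in favour in 40%. This stands as a limit on what the fix gains. It does not repair endpoint 5, because none of those endpoints grades illness between any symptom and hospitalization.

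Three stronger readings are tempting, and the documents do not support them.

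- A reader might infer that the endpoint is biased against the drug. The direction depends on the effect pattern, and the one-level shift shows a pattern in which the contrast points the right way.
- A reader might infer a contradiction with the intention-to-treat sentence in section 6.1. That sentence governs the arm to which each person is assigned. A subset compared by assigned arm does not plainly breach it, although the sentence does not restore those whom the endpoint leaves out.
- A reader might infer that section 6.1 rules out a severity model or adjustment for the stratum. Its outcome lists are given as examples, and it says what the covariates include, not that nothing else enters. The accurate statement is that neither is specified.

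It is also fair to say that this is one of ten secondary endpoints, with no confirmatory claim attached to it.

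**Conclusion.** The point holds as a should-fix matter of analysis population. Objective 5 and endpoint 5 condition on an outcome that the trial hypothesizes treatment will change, and no analysis of endpoint 5 in all randomized participants is planned. The contrast can look harmful when mainly mild cases are prevented (30% to 46% under the assumed rates), can show nothing when mild and moderate illness fall together (30% vs 30%), and can be right under other patterns (30% to 23%). These figures rest wholly on assumed rates, and neither the size nor the direction of any distortion in this trial can be computed from the documents. The distortion is smaller if participants symptomatic at baseline are counted, which the text leaves open. The primary viral-load analysis is unaffected.

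**What to change.** Reword objective 5 and endpoint 5 to compare severity in all randomized participants on an ordinal scale whose lowest level is no symptoms. Before unblinding, fix the scale and one main summary. Either the worst post-baseline level through day 10 (the version illustrated above) or the level at day 10 would serve. The latter misses illness that has already resolved.

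Adjust for the baseline-symptom randomization stratum. Report the proportion at or above each level by arm beside any proportional-odds estimate. State how a day without a self-report is scored, since an admitted participant may not answer. Keep the symptomatic-only comparison as descriptive, and say whether participants symptomatic at baseline belong to it.

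Build the scale from the daily questionnaire, the daily PO2 and the hospital records already planned in section 1.9. Do not rely on the day-10 call: the wording in section 1.9 A leaves unclear whether the medical-status check applies on that day or only on days 3 and 6.

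The cost is a change of wording and a short scale definition, with no new visit or sample. The limits are that power stays low, that the levels can be no finer than what the questionnaire grades (it is not in the documents), and that hospital records need the participant's permission.

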1.4 Preliminary Data

There are data supporting the antiviral activity of NTZ, RBV and HCQ as single agents as summarized in Section 1.2. There is no previous human experience with this triple combination.

1.5 Sample Size Justification

Primary outcome:

Rate of decline in viral load. We expect a gradual decay in viral loads (depending on when in the infection's natural history participants are enrolled. Participants will be detected as being SARS-CoV-2-positive by our screen at varying points in the infection (some early, some late). Based on the 4 manuscripts with measurements, including Hung et al ³¹ and Gautret et al ¹⁹, we can calculate an expected decline rate. One outcome would be a greater than expected fall in viral load in the active arms vs the SoC arm (e.g., 0.3 log₁₀ /day greater decline =0.9 log₁₀ in 3 days).

We will compare rate of decline in viral load Arm 1 (NTZ, RBV + HCQ) to Arm 2 (placebo) with the aim of determining if the combination of NTZ, RBV + HCQ is superior to placebo. We plan to enroll 35 participants in each arm of the trial for a total of 70. We assume data are collected at baseline and 3, 6 and 10 days after enrollment.

Power calculations were obtained from simulated data, where:

- Baseline log10 VL was generated from uniform (3,9) distribution (i.e., at baseline, people were equally likely to have log10 VL anywhere from 3 to 9. This is consistent with Hung et al ³¹
- For the control group, average change per day was set to either -0.3 or -0.4. In Hung et al ³¹ it appears to be about -0.37.
- For the treatment group, the average decline per day was greater (steeper) than the control group by either 0.2 or 0.3. In Hung et al ³¹the difference in slopes appears to be about 0.2
- Within person SD was set to either 0.5 or 1.
- SD of the slope between individuals was set to 0.2. In Hung et al ³¹ the within-group IQR of log10 VL was relatively small, so we do not expect a large amount of variation in slopes between participants.

Power was calculated using the following steps: (1) generate 1000 data sets in each scenario; (2) fit random slope and intercept models to the simulated data; (3) record the proportion of times that the test of the interaction between treatment and slope was rejected.

		treatment effect		
Slope SoC group	SD	-0.2	-0.3	
-0.3	0.5	94	99	
-0.4	0.5	94	99	
-0.3	1	87	99	
-0.4	1	84	99	

Results: Power (%) based on a sample size of 30 per group

In all of these scenarios we would have >80% power to detect a difference in the slope between groups.

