 Adverse Events Based on Signs and Symptoms When collecting AEs, the recording of diagnoses is preferred (when possible) to recording a list of signs and symptoms. However, if a diagnosis is known and there are other signs or symptoms that are not generally part of the diagnosis, the diagnosis and each sign or symptom will be recorded separately.

D. Data Points

Case Report Forms

Completion of the electronic case report forms (eCRFs) will be done in accordance with the instructions outlined in the study specific data capture plan. All eCRFs are considered the primary

data collection document for the study and are stored in REDCap in a confidential format. Only key personnel who are delegated in the delegation of authority log are permitted to make entries, changes, or corrections in the eCRF. All users will complete user training, as required or appropriate per regulations. An audit trail will be maintained automatically by the electronic CRF management system.

Data Points to be collected:

- Baseline medical history
- Treatment compliance
- Daily temperatures
- Symptoms of disease
- Adverse events
- Concomitant medications
- Any standard of care treatments or procedures to manage COVID-19
- Viral load from saliva specimen
- Viral load from mid-turbinate self-nasal swab
- SARS-CoV-2 infections confirmed or suspected in household members

Data Submission Timeline and Forms

Completion of eCRFs will occur within 72 hours of study time point unless otherwise indicated. Baseline (pre-study) eCRFs (e.g., enrollment, medical history, concomitant medications, etc.) will be completed no later than 24 hours after the start of treatment.

E. Study Duration

Study participants will be treated for five (5) days and will then remain on follow-up for up to 28 days after entry into the study. The estimated time to complete the entire study including data analysis is 3-6 months

F. Endpoints

Primary endpoint:

1. Rate of decline in viral load over the 10 days after randomization

Secondary:

- 1. Proportion of participants with virus below LLOQ at day 10
- 2. Proportion of participants asymptomatic at day 10.
- For those who were asymptomatic at baseline: Progression to symptoms--presence or absence of key symptoms: fever ≥ 100.4^o F (38 ^o C); sore throat, cough, shortness of breath, myalgias, vomiting or diarrhea, or change in smell or taste

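### The power simulation has no assay floor and the primary model has no rule for unquantifiable viral loads; with set-to-floor or dropped values the slope difference is diluted and power does not stay above 80% in every scenario.

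*Combined protocol and SAP*

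**What the plan says.** Section 1.5 describes the simulation in full. "Baseline log10 VL was generated from uniform (3,9) distribution". For control, "average change per day was set to either -0.3 or -0.4". The treated decline is steeper by 0.2 or 0.3 per day, the within-person SD is 0.5 or 1, the between-person slope SD is 0.2, and measurements fall on days 0, 3, 6 and 10. Models with random intercepts and slopes are fitted to those data. No step imposes a detection or quantification limit. The power table is for 30 per group, and the text sums it up as "In all of these scenarios we would have >80% power to detect a difference in the slope between groups". On enrolment: "We plan to enroll 35 participants in each arm of the trial for a total of 70".

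For the primary analysis, Section 6.1 says "We will fit a linear mixed effects model, where log10 VL is the outcome", with the treatment-by-time interaction as the test. Its missing-data text concerns participants who drop out before day 10 and ends: "Linear mixed effects models rely on the assumption that missing data are missing at random".

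The endpoint list in Section 1.3 F includes "Proportion of participants with virus below LLOQ at day 10" (secondary 1) and "Number of participants with undetectable viral load and absence of symptoms" (secondary 8). The documents give no value for the LLOQ, no viral-load unit, and no rule for entering a result below the limit into the primary model.

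**The concern.** The plan expects results below the assay limit, but neither the simulation nor the primary model provides for them. A result below the limit has no number to enter in a linear mixed model, so the analyst must replace it or drop it.

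The missing-at-random statement does not cover dropping. A value missing because it lies below the limit is missing because of its own unseen size. Replacing it with the limit flattens the trajectory of anyone who has reached the floor.

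Both rules act more strongly in the arm that clears faster, so if the regimen works they shrink the estimated effect. What is at stake is a working regimen being missed, an understated primary estimate, and a choice of handling rule made after the data exist. The risk of a false positive is not raised.

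**Working it through.** **Inputs.** From Section 1.5: the generator described above. Assumed, because the documents do not give them: two-sided 0.05, and floors of 0, 1 and 2 log10. If the laboratory reports numbers below its LLOQ, the relevant floor is that lower reporting limit.

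**Step 1: reproduce the plan's figure.** With complete balanced data, the interaction test amounts to comparing mean per-person slopes. The sum of squares of days 0, 3, 6, 10 about their mean of 4.75 is 22.5625 + 3.0625 + 1.5625 + 27.5625 = 54.75. The variance of a fitted slope is 0.2² + s²/54.75.

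- s = 0.5: 0.04 + 0.0046 = 0.0446, SD 0.211. At n = 30 the SE of the difference is 0.211 × √(2/30) = 0.0545, so 0.2/0.0545 = 3.67 and power is 95.0% (noncentral t).
- s = 1: 0.04 + 0.0183 = 0.0583, SD 0.241, SE 0.0623, ratio 3.21, power 88.4%.

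The table gives 94/94% and 87/84% for effect -0.2. With no floor, the claim of more than 80% reproduces. (The control slope cannot affect power here, and I cannot reproduce the 84%, but the verdict does not depend on it.) At the planned 35 per arm, no-floor power is 97/97/93/93%.

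**Step 2: how many values fall below a floor.** Mean baseline is 6. Mean day-10 values are 6 - 3 = 3 or 6 - 4 = 2 in control, and 6 - 5 = 1 or 6 - 6 = 0 under treatment with effect -0.2. Simulated share below the floor at day 10, across all scenarios and both effects:

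| Floor (log10) | Control | Treated |
|---|---|---|
| 0 | 14-25% | 36-64% |
| 1 | 24-37% | 50-76% |
| 2 | 36-50% | 63-86% |

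**Step 3: power with a floor, 35 per arm, true effect -0.2.** Columns give within-person SD / control slope.

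| Handling | Floor | 0.5 / -0.3 | 0.5 / -0.4 | 1 / -0.3 | 1 / -0.4 |
|---|---|---|---|---|---|
| None needed | no floor | 97% | 97% | 93% | 93% |
| Set to floor | 0 | 94% | 87% | 85% | 75% |
| Set to floor | 1 | 86% | 69% | 75% | 57% |
| Set to floor | 2 | 68% | 40% | 57% | 35% |
| Dropped | 0 | 96% | 94% | 87% | 76% |
| Dropped | 1 | 95% | 90% | 72% | 69% |
| Dropped | 2 | 90% | 86% | 67% | 53% |
| Left-censored model | 0 | 97% | 97% | 94% | 89% |
| Left-censored model | 1 | 97% | 96% | 91% | 89% |
| Left-censored model | 2 | 95% | 94% | 91% | 89% |

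Mean estimates of the true -0.20 per day are -0.15 to -0.07 (set to floor), -0.18 to -0.13 (dropped) and -0.206 to -0.195 (censored).

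The set-to-floor rows use 20,000 trials per cell, per-person least-squares slopes and a t test on 68 df. The dropped and censored rows use 250 trials per cell, maximum-likelihood mixed models and sandwich SEs; Monte Carlo SE is about 2 points near 90% and 3 points near 55%.

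**Step 4: true effect -0.3, same column order.** Set to floor gives 99.9/98/99/94% (floor 0), 98/87/94/78% (floor 1) and 87/55/79/49% (floor 2). In the last cell alone, at floors 0/1/2, dropping gives 96/92/79% and the censored model 100/100/99% (150 trials per cell).

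**Step 5: no true effect.** Rejection is 4.8-5.2% (set to floor, all scenarios, floors 0-2), 4.4-6.0% (dropped) and 4.0-5.2% (censored); the last two were checked in two scenarios at floor 2.

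**The case against.** The strongest reply is that the quoted sentence is true of the scenarios it lists, that Section 6.1 is silent on values below the limit rather than wrong about them, and that the loss comes from handling rules I supplied. With a censored model, 70 participants keep at least 89% power in every effect -0.2 cell at floors 0-2. All of that is correct. It locates the fault in the missing rule rather than in the sample size, but the plan as written does not specify the analysis that would rescue the claim.

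Setting values to the limit itself is also a harsh rule. At 35 per arm and effect -0.2, half-limit substitution at floor 0 leaves the worst cell at about 79%, a marginal shortfall. With a floor of 2 and values set to 0 log10, power is 90/77/79/65%. Under dropping, every SD 0.5 cell stays above 80%. Effect -0.3 is much more robust. These points reduce the size of the loss. They do not restore the statement about all scenarios.

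The control slope (about -0.37) and the difference (about 0.2) were read from a cited trial's measured data. If those data already reflect an assay limit, part of the dilution is already in the 0.2, and my figures overstate the additional loss. The documents do not settle this. Even so, a generator that yields many values below 0 log10 does not represent measured data.

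Finally, the censored model extrapolates linear decline below the limit, and it was tested only on data generated that way.

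**Conclusion.** The concern holds. Once a floor of 0 to 2 log10 is imposed on the plan's own generator, at least one scenario falls below 80% power at 35 per arm, whether values are set to the floor or dropped. Worst-cell power for effect -0.2 runs from 76% down to 35%. The scenarios nearest the slopes that Section 1.5 reads from its cited trial (control -0.4, difference -0.2) are the hardest hit under set-to-floor handling, where the true -0.20 per day shrinks to between -0.13 and -0.07.

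The direction is certain for both handling rules. The size depends on the unstated limit, on the rule chosen, and on a two-sided 0.05 test, which the plan also does not state. The harm is an understated effect and lost power for the primary endpoint. This should be corrected before analysis.

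**What to change.** 1. In Section 6.1, state the laboratory's reporting limit and its unit. Make the primary model a left-censored (Tobit-type) linear mixed model with the planned fixed effects and random intercept and slope, in which each result below the limit contributes P(Y < limit). Keep the planned uncensored model as a sensitivity analysis, with its substitution rule written down.
2. In Section 1.5, rerun the simulation with that limit imposed and that model fitted. Restate power for both effect sizes at 35 per arm, and replace the summary sentence with what the new table shows. Some cells may fall below 80%: a separate censored-model check at 30 per arm and floor 2 gave about 79% and 83% in the two SD 1 cells at effect -0.2.

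The cost is revised wording, one extra model and a rerun of the simulation, with no added participants or samples. The downsides are reliance on linear decline continuing below the limit, which the uncensored sensitivity analysis helps to expose, and a stated power lower than the no-floor figures.
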